Primary Outcomes	
To determine whether the addition of belimumab to the standard of care (SOC: alemtuzumab and steroid induction with mycophenolic acid and tacrolimus maintenance immunosuppression) is safe and effective in preventing de novo DSA production 1, 3, 6, 9, and 12 months.

Secondary Outcomes	
Secondary endpoints will be 1) graft survival and function as determined by serum creatinine/eGFR and urine protein at 1, 3, 6, 9, and 12 months 2) rates of acute cellular and antibody mediated rejection at 1, 3, 6, 9, and 12 months and 3) the nature, frequency, and severity of serious and non-serious adverse events \geqGrade 2 per Common Terminology Criteria for Adverse Events (CTCAE), Version 4.0.

Eligibility Criteria	
Subjects 18-60 years of age receiving a living donor kidney transplant who are sensitized: PRA>0 and/or sum DSA<1000 MFI.

Inclusion

- Male or female subjects 18-60 years of age **Criteria**
- Planned to receive a living donor kidney transplant
- Sensitized patients: Positive DSA with sum MFI <1000, and/or PRA>0%
- Subjects must be capable of understanding the purpose and risks of the study and must sign a statement of informed consent.

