- **B Lymphocyte Analysis:** B-cell FACS panels will be used to measure changes over the course of therapy in the transitional, naïve, memory and plasma cell compartments. For the subsets of interest, absolute numbers of cells and proportions relative to all B cells for the individual subsets will be determined, as will activation status. Specifically we will address peripheral transitional, naive, memory and plasma cell populations prior to transplant and at 1, 3, 6, 9, and 12 months post-transplant. Further exploratory analyses will include the expression of BLyS receptors (BR3, TACI and BCMA) on B cells, frequency of alloreactive B cells (using tetramers) and an analysis of the effect of belimumab on IL-10 secreting B regulatory cells. Again these assessments will be performed prior to transplant and at 1, 3, 6, 9, and 12 months post transplant
- **T Lymphocyte Analysis:** Similar assessments will be made of T cell subsets prior to transplant and at 1, 3, 6, 9, and 12 months post-transplant. Specifically we will evaluate activated T cell and T regulatory cell populations.

- **Cytokine Analysis:** Quantification of serum BLyS and APRIL levels and cytokines/chemokines associated with T-helper skewing or activation will be performed prior to transplant and at 1, 3, 6, 9, and 12, months posttransplant
- **Immunoglobulin Analysis:** Quantification of total serum levels of Immunoglobulin levels (IgM, IgA, and IgG) will be performed prior to transplant and at 1, 3, 6, 9, and 12 months post-transplant.

7. Safety Assessments

The patient will be evaluated for safety, and adverse events will be documented according to the procedures of the investigational site. The investigator will determine the relationship of the events to the administration of belimumab.

Patients will be clinically assessed for suicidal ideation and/or behavior at each visit. If patient exhibits suicidal ideations or it is verbally expressed, the PI will enter a note and refer the patient to a psychiatrist.

Expected Adverse Events (AEs) \geq Grade 2, and all unexpected adverse events will be documented, graded, and assessed for causality to belimumab by the Principal Investigator.

All Serious Adverse Events (SAEs) will be reported to GlaxoSmithKline within 24 hours. SAEs that meet the FDA and IRB reporting criteria will be reported within the specified timeframe. Serious Adverse Events will be documented, graded, and assessed for causality to belimumab by the Sponsor-Investigator.

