7.1 Adverse Events

An Adverse Event (AE) is defined as any new untoward medical occurrence or worsening of a pre-existing medical condition in a patient or clinical investigation subject administered an investigational (medicinal) product and that does not necessarily have a causal relationship with this treatment. An AE can therefore be any unfavorable and unintended sign (including an abnormal laboratory finding, for example), symptom, or disease temporally associated with the use of investigational product, whether or not considered related to the investigational product.

Adverse events are defined as any signs (including abnormal diagnostic test result) or medical diagnoses noted by medical personnel, or symptoms reported by the subject, regardless of relationship to study drug, that:

1. have onset anytime after the start of study drug treatment, or
2. increase in severity during drug treatment or procedures (pre-existing signs, symptoms or diagnoses).

Subjects will be interviewed in a non-directed manner to identify potential adverse events. This occurrence of an adverse event will be based on changes in the subject's physical examination, laboratory results, and/or signs and symptoms. Only those abnormal laboratory results that are considered clinically significant will be evaluated as a potential adverse event. All adverse events \geq Grade 2 per CTCAE, including observed or volunteered problems, complaints, or symptoms are to be recorded, if they are thought to be related to the study drug or study procedures. All documented adverse events will be monitored until they are resolved or are clearly determined to

be due to a subject's stable or chronic disease condition or intercurrent illness(es). Each adverse event is to be evaluated for duration, intensity and causal relationship with the study medication or other factors.

Adverse events will be graded according to the Common Terminology Criteria for Adverse Events (CTCAE), Version 4.0.

Grade refers to the severity of the AE. The CTCAE displays Grades 1 through 5 with unique clinical descriptions of severity for each AE based on this general guideline:

Grade 1 Mild; asymptomatic or mild symptoms; clinical or diagnostic observations only; intervention not indicated.

Grade 2 Moderate; minimal, local or noninvasive intervention indicated; limiting ageappropriate instrumental ADL.

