Grade 3 Severe or medically significant but not immediately life-threatening; hospitalization or prolongation of hospitalization indicated; disabling; limiting self care ADL

Grade 4 Life-threatening consequences; urgent intervention indicated.

Grade 5 Death related to AE.

7.2 *Serious Adverse Events*

A Serious Adverse Event (SAE) is any untoward medical occurrence that at any dose:

- Is fatal
- Is life-threatening
- Requires or prolongs inpatient hospitalization
- Results in persistent or significant disability/incapacity
- Is a congenital anomaly/birth defect

The inpatient stay following the transplantation procedure will be considered SAE only if prolonged for more than 14 days.

A medical event that may not be immediately life-threatening or result in death or hospitalization but may jeopardize the subject or may require intervention to prevent a serious outcome, may also be considered serious (e.g. intensive treatment in an emergency room or at home for allergic bronchospasm; blood dyscrasias or convulsions that do not result in hospitalization; or development of drug dependency or drug abuse). Medical and scientific judgment must be exercised when classifying events as serious. The Investigator must determine both the intensity of the serious adverse event and the relationship of the event to the administration of study medications.

7.2.1 *Reporting*

It is the responsibility of the Investigator to promptly notify the Institutional Review Board of all unanticipated problems involving risk to human research subjects. All serious adverse events including fatal or life-threatening events experienced by study participants in the study will be reported to GlaxoSmithKline, Inc., to ICTR DMC, the FDA per applicable regulations, and the UW IRB according to current IRB guidelines.

Adverse Events that are:	Notify:
Serious Suspected/Related* Unexpected	GSK Medical Monitor: Within 24 hours DMC: Within 14 business days HSIRB: Within 14 business days FDA and all participating institutions as soon as possible, but no later than 15 calendar days after learning of the event
Life threatening or Fatal Suspected/Related* Unexpected	GSK Medical Monitor: Within 24 hours DMC: Within 24 hours HSIRB: Within 1 business day of learning of the event. FDA: Within 7 calendar days of learning of the event
*Events that are possibly, probably, or definitely related meet the criteria for "Suspected/Related"	

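### Section 7.1 ties the recording of Grade 2 or higher adverse events to suspected relatedness, while Section 7 and the adverse-event endpoint have no such condition, so non-serious events judged unrelated can be lost

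*Combined protocol and SAP*

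**What the plan says.** Section 7.1 contains three statements that bear on which events are captured.

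- It defines adverse events as signs, diagnoses or symptoms "regardless of relationship to study drug".
- It then sets the recording rule for events of CTCAE Grade 2 or higher: observed or volunteered problems, "complaints, or symptoms are to be recorded, if they are thought to be related to the study drug or study procedures".
- It ends by requiring each event to be evaluated for duration, intensity and "causal relationship with the study medication or other factors".

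The opening of Section 7 gives a different rule. Expected events of Grade 2 or higher, "and all unexpected adverse events will be documented, graded, and assessed for causality to belimumab by the Principal Investigator". On serious events, Section 7 says "All Serious Adverse Events (SAEs) will be reported to GlaxoSmithKline within 24 hours", and Section 7.2.1 likewise covers "All serious adverse events including fatal or life-threatening events experienced by study participants".

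The endpoint is worded almost identically in the synopsis, Section 3.2.2 and Section 9: "the nature, frequency, and severity of serious and non-serious adverse events" of Grade 2 or higher. None of the three restricts it to related events.

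On follow-up, Section 5.1.3 collects study data in REDCap for one year after transplant. Section 7 collects health information and monitors safety for 12 months after study treatment is discontinued, or for 12 months from transplant if the graft fails before month 6.

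**The concern.** Attribution is used in two incompatible ways. In Section 7 and the endpoint it is a property assessed after an event has been recorded. In the recording sentence of Section 7.1 it is a condition for recording the event at all. No text says which section takes precedence.

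This matters because the synopsis makes safety part of the primary objective and adverse events of Grade 2 or higher are a listed secondary endpoint. The analysis is descriptive and there is no concurrent control arm, so whatever is recorded becomes the result.

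The attribution itself is uncertain here. The investigator makes it in an open-label study, and Section 1.3 states that belimumab has not previously been combined with alemtuzumab or tacrolimus. Every patient also receives background drugs with overlapping toxicity. An infection or leukopenia put down to standard of care is the kind of event that the Section 7.1 condition could leave out.

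**Working it through.** The plan gives no calculated figure on this point, so there is nothing to reproduce. The check applies each rule to the same event.

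**Step 1. Apply the rules.**

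| Text | Non-serious, Grade 2 or higher, expected or unexpected, judged unrelated | Serious, judged unrelated |
|---|---|---|
| Section 7 | Documented, graded, causality assessed | Reported |
| Section 7.1, definition | Is an adverse event | Is an adverse event |
| Section 7.1, recording rule | Not required to be recorded | Not required by this sentence |
| Section 7.2.1 | Not addressed | Reported |
| Synopsis, Sections 3.2.2 and 9 | Counted in the endpoint | Counted in the endpoint |

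Sections 7 and 7.2.1 capture serious events whatever the attribution. The gap is confined to non-serious events judged unrelated, and it opens only if Section 7.1 is the rule the site follows.

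**Step 2. Width of the gap.** The table in Section 7.2.1 has a footnote: "Events that are possibly, probably, or definitely related meet the criteria for" the suspected or related category. If that definition carries over to Section 7.1, only events judged clearly unrelated drop out. The footnote belongs to expedited reporting, however, and Section 7.1 does not refer to it.

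**Step 3. Effect of one omission.** With n = 5 (synopsis), leaving out one patient whose only event of a given type goes unrecorded changes that event's reported frequency by 1/5 = 20 percentage points. This is the effect of a single omission, not an estimate of how many will occur.

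**Step 4. Where the condition could act.** Section 1.3 gives 57% leukopenia and 32% infection after alemtuzumab induction in 251 recipients. If those rates applied here, 5 × 0.57 = 2.85 and 5 × 0.32 = 1.6 patients would be expected to have such events. The documents give neither grade, seriousness nor attribution for them, so this shows where attribution will matter and not how many events would be lost.

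**Step 5. Follow-up period (the lesser point).** Take 12 months as 52 weeks. Section 5.1.3 then ends at Week 52. Section 7 ends 52 weeks after the week in which treatment stops, so the difference equals that stopping week.

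- Treatment stopped after Day 0 only: 0 + 52 = Week 52; difference 0 weeks.
- Last dose at Week 16: 16 + 52 = Week 68; 68 − 52 = 16 weeks.
- Last dose at Week 20, as scheduled: 20 + 52 = Week 72; 72 − 52 = 20 weeks.
- Last dose at Week 22, after one 2-week delay allowed by Section 5.1.2: 22 + 52 = Week 74; 74 − 52 = 22 weeks.

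These are examples, not limits. For a graft lost before month 6, Section 7 itself counts from transplant and the difference disappears.

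**The case against.** The strongest reply is that Section 7.1 says *if*, not *only if*. A site that records everything under Section 7 also satisfies Section 7.1, so the clause can be read as a minimum beneath a broader rule. Other text supports that reading. Section 6.3.2 has adverse events recorded before each dose with no relatedness condition, and Appendix A schedules them through Month 12. Section 7.1 asks for non-directed interviews and follows events until they resolve or are traced to chronic or intercurrent illness. On this view one clause is a drafting slip and little would be lost in practice.

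There are also other safeguards. Section 6.3 records changes in health at visits. Section 8.4 says infections may be entered in REDCap. Section 7.3 has the DMC review all adverse events and allows it to look at source documents. No termination trigger in Section 3.6 depends on counts of non-serious events.

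Much of this stands, and it limits the likely consequence. It does not remove the clause. The conditional reading is at least as natural as the minimum reading, and nothing tells the site which to use. The surrounding text shows that the clause is the outlier, which is a reason to correct it. The safeguards are optional or indirect: an event noted in a chart but not entered as an adverse event does not reach the endpoint, and the DMC would find it only through a source review that may not take place.

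On follow-up, Sections 5.1.3 and 7 may describe different things (study data in REDCap against health information from routine care). That point is therefore held with less certainty, and the main finding does not depend on it.

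**Conclusion.** The concern holds. As written, the recording rule in Section 7.1 is inconsistent with the definition and causality step in the same section, with Section 7, and with the endpoint and its planned analysis. If it is followed, non-serious events of Grade 2 or higher judged unrelated can be missing from the secondary endpoint, and all-cause frequency would tend to be understated.

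Confidence is high about the inconsistency and lower about its practical effect. The loss is zero if the site follows Section 7, and may be small if it follows Section 7.1 with possibly related events counted as related. Otherwise the documents do not allow an estimate. This should be fixed. It does not threaten the capture of serious events or the termination rules.

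The difference between Sections 5.1.3 and 7 on follow-up is present in the text, but it is secondary.

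**What to change.** Delete the relatedness clause from the recording sentence in Section 7.1, so that Sections 7 and 7.1 state one rule:

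- All events of Grade 2 or higher and all serious events are recorded regardless of attribution.
- Unexpected events are recorded as Section 7 already provides. Because Section 7 sets no grade limit for these, add that unexpected Grade 1 events are recorded but fall outside the Grade 2 or higher endpoint.
- Causality is a separate recorded item for each event, so that all-cause and related events can both be reported.

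Separately, reconcile Sections 5.1.3 and 7 on the safety follow-up period and state it once.

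The cost is a short amendment and possibly a few more adverse-event entries for 5 patients. Reconciling the follow-up period is a wording change; any further record collection depends on how it is settled.

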8.1 Statement of Compliance

This trial will be conducted in compliance with the protocol, current Good Clinical Practices (GCP), adopting the principles of the Declaration of Helsinki, and all applicable regulatory requirements.

Prior to study initiation, the protocol and the informed consent documents will be reviewed and approved by an appropriate ethics review committee or Institutional Review Board (IRB). Any amendments to the protocol or consent materials must also be approved before they are implemented.

8.2 Informed Consent

The informed consent form is a means of providing information regarding the trial to a prospective participant and allows for an informed decision about participation in the study. All participants must read, sign and date a consent form prior to participation in the study, taking study drug and/or undergoing any study-specific procedures.

The informed consent form must be updated or revised whenever important new safety information is available, whenever the protocol is amended, and/or whenever any new information becomes available that may affect a patients' participation in the trial.

A copy of the informed consent will be given to a prospective participant for review. The Study Investigator or a designee of the Investigator will review the consent and answer any questions that the potential participant may have. The participant will be informed that their participation is voluntary and they may withdraw from the study at any time, for any reason.

8.3 Recruitment Methods

Patients being evaluated for a living donor kidney transplant who meet the selection criteria will be contacted by study personnel. The potential subjects will be contacted to briefly explain the study and ask if they would mind to review a consent form. If the potential subject agrees, the study personnel go through the consent form and answer questions. At the end, the study personnel will ask the potential subject if they would like to be in the study. If a potential subject replies yes, study personnel will have them review and sign the consent form. Study personnel will meet them prior to any study related procedures to obtain consent.

8.4 Privacy and Confidentiality

A patient's privacy and confidentiality will be respected throughout the study. Each study participant will be assigned a sequential identification number and these numbers rather than names will be used to collect, store and report participant information.

All data collected for this study from subjects will be done in a private patient exam room. Data may be extracted from the subject's medical record (paper/electronic) by the Publications and Clinical Research Service (PACRS), study coordinators and the PIs. Data necessary to achieve the aims of the research will be the only data collected from the subjects or the medical records. Source documents for data, including signed ICF and Research Authorization forms, will be maintained in subject study specific binders. Subjects are identified on all documents and samples by a study specific identifier and study assigned number. These binders are stored in the locked office of the Office of Clinical Trials coordinator.

All paper files and computers are located in an office that is staffed during the day, and locked when staff is not present. Electronic source documents and data analysis will be created and stored on the Department of Surgery secure password protected network server.

Study personnel will have access to the OnCore registration log that links identifiable subject information to the assigned subject study code. Only key personnel assigned to the study will have access to this information.

Data including treatments, eGFR, AEs, deaths, infections (bacterial/viral/fungal), or sepsis may be included in REDCap for Data Safety Monitoring.

No data or subject information will be released to the funding institution as this is an investigator initiated study and all data belongs solely to the investigator. No data will be stored on laptops or portable devices.

8.5 Records Retention

The investigator will retain, in a confidential manner, all data pertinent to the study for all treated subjects. The investigator will retain source documents and accurate case histories that record all observations and other data pertinent to the investigation (e.g., the medical record) for the maximum period (7 years) or 2 years after completion/termination of the IND with the FDA, as required by applicable regulations and guidelines or following institutional procedures.

9. Statistical Section

A biostatistician in the UW Madison Department of Surgery or the Division of Nephrology will perform the statistical analyses. The primary outcome and secondary outcomes will be assessed using descriptive statistics. Specifically, we will describe the rate of de novo DSA development, graft survival and function as determined by serum creatinine/eGFR and urine protein, rates of acute cellular and antibody

mediated rejection, and the nature, frequency, and severity of serious and non-serious adverse events \geq Grade 2.

10. References

1. Sellares J, de Freitas DG, Mengel M, et al. Understanding the causes of kidney transplant failure: the dominant role of antibody-mediated rejection and nonadherence. *American Journal of Transplantation*. 2012;12(2):388-399.
7. Redfield RR, 3rd, Rodriguez E, Parsons R, et al. Essential role for B cells in transplantation tolerance. *Current Opinion in Immunology*. 2011;23(5):685-691.

11.0 Appendix A (Schedule of Events)

	CAMPBEL Trial												
	Screen	Hospitalization	Outpatient Visit										
			Day of Transplant (Day 0)	1 Week	2 Weeks	4 Weeks Month 1	8 Weeks	Weeks Month 3	Weeks	Weeks	Weeks Month 6	Weeks Month 9	Weeks Month 12
	≤30 days prior to transplant	May be same day as screening		□ 3d	□ 3d	□ 3d	□ 3d	□ 3d	□ 3d	□ 3d	□ 7d	□ 7d	□ 7d
Informed Consent	X												
Demographics	X												
Medical History	X												
Physical Exam	X			X	X	X	X	X	R	R	X	X	X
Vital Signs (+ weight) ¹	X	XΔ		X	X	X	X	X	R	R	X	X	X
Hematology ^{2*}	X	X		X	X	X	X	X	R	R	X	X	X
Comprehensive Metabolic Panel*	X	X		X	X	X	X	X	R	R	X	X	X
Urine Protein/ Creatinine*	X	X		X	X	X	X	X	R	R	X	X	X
Serum pregnancy test ^{3**}	X	X			R ⁸	R ⁸	R ⁸	R ⁸	R ⁸	R ⁸			
PRA*	X	X				X		X			X	X	X
Anti HLA antibodies by Luminex*	X	X				X		X			X	X	X
ECG*	X												
Viral Serology ^{3*}	X	X											
Immunoglobulin Panel: IgG, IgA, IgM by clinical lab*	X					X	X	X	X	X	X	X	X
Tacrolimus Trough				X	X	X	X	X	X	X	X	X	X
Steroid Taper		X											
Alemtuzumab		X											
Tacrolimus/ Mycophenolic Acid ⁹		X	X	X	X	X	X	X	X	X	X	X	X
Belimumab ⁴		R ⁴		R ⁴	R ⁴	R ⁴	R ⁴	R ⁴	R ⁴	R ⁴			
Kidney biopsy ⁵		X											X
Adverse Events ⁶		R ⁶	R ⁶	R ⁶	R ⁶	R ⁶	R ⁶	R ⁶	R ⁶	R ⁶	R ⁶	R ⁶	R ⁶
Con Meds	R		R	R	R	R	R	R	R	R	R	R	R
Cytokine Analysis ⁷	R	R			R		R			R	R	R	R
T Lymphocyte Analysis ⁷	R	R			R		R			R	R	R	R
B Lymphocyte Analysis ⁷	R	R			R		R			R	R	R	R
Immunoglobulin Analysis (IgM, IgA, IgG) ⁷	R	R			R		R			R	R	R	R
BAFF/APRIL Analysis ⁷	R	R			R		R			R	R	R	R

¹ Vital signs include temperature, blood pressure, pulse and respiratory rate recorded prior to each study drug dose.

² Hematology: CBC and differential

³ HIV, HBsAg, anti-HBc, anti-HBs antibodies, hepatitis C antibody, herpes simplex virus, CMV, Epstein Barr virus, and varicella zoster virus per standard of care. For eligibility assessment, if the screening virology results for HIV, HCV and HBV are not available prior to transplantation then the most recent historical result (within the last 6 months) will be used. Per standard of care, the viral serology tests for CMV, Epstein Barr Virus, and varicella are not to be repeated once found positive.

⁴ Belimumab infusion ⁵ Kidney biopsy will be performed at time of transplant per standard of care, and at 1 year to assess histologic response per standard of care.

⁶ Adverse events recorded prior to each study drug dose and will include subject reports of changes in sleep patterns, anxiety and suicidality

⁷ If subject consents: Blood collected for future research lab processing and analysis by transplant research lab ⁸ For Women of Child-bearing potential, within 48 hours prior to transplant and prior to each dose of belimumab. ⁹ Tacrolimus and Mycophenolic Acid start date and dosing may be adjusted per physician discretion

*Clinical labs drawn on the day prior to transplant (day -1) do not need to be repeated unless clinically indicated

X=Standard of Care

R= Procedure for Research Purposes

A Blood pressure and Heart rate will be recorded within 15 minutes prior to infusion, 15±5 minutes after beginning infusion and 15±5 after completion of infusion
